7.2.3.3 Non-dilated/Dilated Fundus Examination

Fundus examination must be conducted after BCVA, slit lamp biomicroscopy, and conjunctival swab for bacterial culture has been collected.

A non-dilated fundus examination will be performed in all subjects with the exception of infants and uncooperative small children during the study as outlined in [Table 1](#).

Observations will be graded as normal or abnormal. Abnormal findings will be described.

The following will be examined:

- Vitreous
- Optic Nerve
- Macula

Clinically significant changes should be recorded in the source and on the eCRF as an AE.

If a non-dilated fundus exam is attempted and is not feasible, a dilated fundus exam should be conducted. The test should be conducted the same way (either dilated or non-dilated) at both Visits 1 and 5 (or ET).

For infants and small children in whom a fundus examination cannot be done, a red reflex exam will be conducted in accordance with the AAP Policy Statement for Visual System Assessment in Infants, Children, and Young Adults by Pediatricians ([Donahue and Baker, 2016](#); [American Academy of Pediatrics, 2016](#); located in the Study Operations Manual). Observations will be graded as normal or abnormal. Abnormal findings will be described. The red reflex should be normal (present and symmetrical for both eyes) at the screening/baseline visit.

7.2.3.4 Adverse Event Collection

At each study visit, subjects will be questioned in a general way to ascertain if AEs have occurred since the previous visit (eg, "Have you had any health problems since your last visit?"). Adverse events are collected from the time informed consent is signed. (Please refer to Section 8, Adverse and Serious Adverse Events Assessment.) Any AE that occurs after the first dose of investigational product instillation will be considered a treatment-emergent AE (TEAE).

Adverse events may also be determined by the investigator during study examinations as mentioned in previous sections.

7.2.3.5 Microbiology Laboratory Evaluations

All laboratory assays will be performed according to the laboratory's normal procedures.

All bioanalytical assays for the study will be validated following Food and Drug Administration (FDA)/International Conference on Harmonisation (ICH) guidelines, based on the method's intended use. The lab will only receive sample identification numbers and collection dates, and the lab results will then be transferred to the central lab for data analysis. The lab will not receive any information on subject treatment assignment.

One swab sample from inferior conjunctival cul-de-sac of each eye will be collected at all study visits for all bacterial testing. An additional sample will be collected from each eye at Visit 1 for qualitative detection of herpes simplex virus (HSV). This sample will also be used for PCR qualitative detection of chlamydia and gonorrhea in subjects <2 months of age.

Bacterial eradication as well as antibiotic sensitivity will be determined based on bacterial cultures using standard microbiological laboratory procedures.

7.2.3.6 Pregnancy Test

A urine pregnancy test is performed on all females of childbearing potential at Visits 1 and 5, or if pregnancy is suspected. Urine pregnancy test kits will be provided by the sponsor and read on site by qualified site personnel.

7.2.3.7 Health-related Quality of Life Assessments

Ocular discomfort associated with conjunctivitis symptoms will be assessed through the ocular discomfort scale (ODS). The ODS is composed of 3 items: pain, itching, and foreign body sensation. All items will be evaluated using a 0-10 scale. A separate scale will be administered for children younger than 8 years of age. Please see the Study Operations Manual for a detailed description of this assessment.

8. ADVERSE AND SERIOUS ADVERSE EVENTS ASSESSMENT

8.1 Definition of Adverse Events, Period of Observation, and Recording of Adverse Events

An AE is any untoward medical occurrence in a clinical investigation subject administered a pharmaceutical product and that does not necessarily have a causal relationship with this treatment. An AE can therefore be any unfavorable and unintended sign (including an abnormal laboratory finding), symptom, or disease temporally associated with the use of a medicinal (investigational) product, whether or not related to the medicinal (investigational) product (ICH Guidance E2A 1995).

All AEs are collected from the time the informed consent is signed until the defined follow-up period stated in Section 7.1.3. This includes events occurring during the screening phase of the study, regardless of whether or not investigational product is administered. Where possible, a diagnosis rather than a list of symptoms should be recorded. If a diagnosis has not been made, then each symptom should be listed individually. All AEs should be captured on the appropriate AE pages in the CRF and in source documents. In addition to untoward AEs, unexpected benefits outside the investigational product indication should also be captured on the AE CRF.

All AEs must be followed to closure (the subject's health has returned to his/her baseline status or all variables have returned to normal), regardless of whether the subject is still participating in the study. Closure indicates that an outcome is reached, stabilization achieved (the investigator does not expect any further improvement or worsening of the event), or the event is otherwise explained. When appropriate, medical tests and examinations are performed so that resolution of event(s) can be documented.

8.1.1 Severity Categorization

The severity of AEs must be recorded during the course of the event, including the start and stop dates for each change in severity. An event that changes in severity should be captured as a new event. Worsening of pre-treatment events, after initiation of investigational product, must be recorded as new AEs (for example, if a subject experiences mild intermittent dyspepsia prior to dosing of investigational product, but the dyspepsia becomes severe and more frequent after first dose of investigational product has been administered, a new AE of severe dyspepsia [with the appropriate date of onset] is recorded on the appropriate CRF).

The medical assessment of severity is determined by using the following definitions:

Mild: A type of AE that is usually transient and may require only minimal treatment or therapeutic intervention. The event does not generally interfere with usual activities of daily living.

Moderate: A type of AE that is usually alleviated with specific therapeutic intervention. The event interferes with usual activities of daily living, causing discomfort but poses no significant or permanent risk of harm to the research subject.

Severe: A type of AE that interrupts usual activities of daily living, or significantly affects clinical status, or may require intensive therapeutic intervention.

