11.1 Adverse Events

AEs will be coded using MedDRA version 19.1. Any AE that occurs after the first dose of investigational product instillation will be considered a treatment-emergent adverse event (TEAE).

An overall summary of the number of subjects with TEAEs will be presented, including the number and percentage of subjects with any TEAEs, ocular TEAEs, non-ocular TEAEs, TEAEs leading to death, serious TEAEs, TEAEs related to investigational product and TEAEs leading to discontinuation of investigational product as well as the total number of events in each category.

The number and percentage of subjects reporting TEAEs in each treatment group and across all subjects will be tabulated by SOC and preferred term as well as by SOC, preferred term, and maximum severity. TEAEs considered related to investigational product will also be summarized by SOC and preferred term. If more than 1 AE occurs with the same SOC/preferred term for the same subject, then the subject will be counted only once for that SOC/preferred term using the most severe and most related occurrence for the summarization by severity and by relationship to investigational product, respectively. The incidence of common TEAEs ($\geq 5\%$ of subjects in any treatment group) will also be summarized by SOC and preferred term. Serious TEAEs, TEAEs leading to discontinuation of investigational product and TEAEs leading to death, will be summarized by SOC, preferred term and treatment group and across all subjects. The number and percentage of subjects reporting local tolerability TEAEs in each treatment group and across all subjects will also be tabulated. Local tolerability TEAEs (overall, related to IP and not related to IP) will be tabulated by SOC and preferred term. Preferred terms that are considered to be local tolerability AEs will be provided by global drug safety (GDS) before database lock. Separate tables will be generated for ocular TEAEs and non-ocular TEAEs. For all above tables, ocular TEAEs will be summarized at subject level and also by study eye, fellow eye and both eyes.

Listings of all TEAEs will be provided by subject.

Pre-treatment events (captured on the AE form that occurred prior to the first dose of investigational product) will be listed by subject but not tabulated.

Imputed dates, severity and relationship to investigational product (see Section 18.7, 18.8 and 18.9 respectively for imputation rules) will be marked in the listings.

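### Each severity change is recorded as a new adverse event and no rule links the records, so one post-dose episode can be counted several times in the TEAE event totals

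*Protocol*

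**What the plan says.** **Recording.** Protocol 8.1.1 requires the following: "The severity of AEs must be recorded during the course of the event, including the start and stop dates for each change in severity". It then adds: "An event that changes in severity should be captured as a new event". Neither sentence restricts the direction of change. The next sentence covers events present before treatment and names only one direction: "Worsening of pre-treatment events, after initiation of investigational product, must be recorded as new AEs".

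**Benefits.** Protocol 8.1 opens its definition with "An AE is any untoward medical occurrence in a clinical investigation subject administered a pharmaceutical product". Later in the same section it says: "In addition to untoward AEs, unexpected benefits outside the investigational product indication should also be captured on the AE CRF".

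**What is treatment-emergent.** SAP 11.1 uses timing only: "Any AE that occurs after the first dose of investigational product instillation will be considered a treatment-emergent adverse event (TEAE". Protocol 7.2.3.4 and the synopsis give the same rule. None of them requires the event to be new or worse.

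**What is counted.** The overall summary in SAP 11.1 gives subjects with TEAEs by category (any, ocular, non-ocular, serious, related, and so on) "as well as the total number of events in each category". Protocol 9.9 goes further and plans the number of TEAEs overall, by SOC, by preferred term and by treatment group. For subject counts, SAP 11.1 takes each subject once per SOC and preferred term, at the most severe and most related occurrence.

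**The concern.** The recording rule and the counting rule are each workable alone. Together they turn every severity step after first dose into a further TEAE. A step down counts the same as a step up, so an event that eases in stages adds more to the total than one that stays at a single grade until it stops.

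Safety and tolerability against PVP-I and placebo is a stated secondary objective (Protocol 2.2.3), and SAP 11.1 plans separate tables for local tolerability TEAEs. A reader of the overall summary will take a number of TEAEs as a number of episodes. If severity changes more often in one arm than in another, event totals will differ between arms even where the number of episodes does not.

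**Working it through.** The plan gives no figure to reproduce. The check applies the written rules to simple cases.

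**Inputs**
- One new record per severity change, each with its own dates (Protocol 8.1.1).
- A TEAE is any AE after first dose (SAP 11.1; Protocol 7.2.3.4).
- Events are counted without linkage (SAP 11.1; Protocol 9.9). SAP 18.7 to 18.9 deal only with missing dates, severity and relationship.
- Subjects are counted once per SOC and preferred term (SAP 11.1).

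**Formula.** For an episode that starts after first dose and changes severity *k* times:

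TEAEs counted = 1 + *k*; subjects counted for that term = 1.

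| Episode | AE records | TEAEs as written | Subjects with TEAE of that term | TEAEs if linked and new-or-worsened |
|---|---|---|---|---|
| Post-dose, moderate then mild | 2 | 2 | 1, at moderate | 1 |
| Post-dose, mild, moderate, mild | 3 | 3 | 1, at moderate | 1 |
| Pre-dose mild, moderate after dosing | 2 | 1 | 1 | 1 |
| Pre-dose moderate, mild after dosing, general sentence of 8.1.1 applied | 2 | 1 | 1, if no other TEAE of that term | 0 |
| Same, worsening-only sentence applied | 1 | 0 | 0 | 0 |

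The first two rows show the effect on event totals, with subject counts protected. The last two rows show the one situation in which subject incidence could move. There the two adjacent sentences of 8.1.1 point different ways.

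**Size, on an assumption.** Neither document gives a rate of severity change. For post-dose events:

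events counted / episodes = 1 + mean number of changes per event

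- mean 0.25: 1 + 0.25 = 1.25
- mean 0.5: 1 + 0.5 = 1.5
- mean 1: 1 + 1 = 2

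To show what a difference between arms would do, take two arms with the same number of episodes, one at a mean of 0.25 and the other at 1. Their event totals would stand in the ratio 2 / 1.25 = 1.6. The documents do not say whether such a difference exists or which arm it would affect.

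**Benefit records.** The AE definition covers untoward occurrences, and Protocol 8.1 names benefits as something in addition to them. SAP 11.1 counts AEs, so on the wording a benefit is not a TEAE. But the record sits on the AE form, and neither document mentions a flag or an exclusion. If such a record with a post-dose start were left in the AE data with blank fields, SAP 18.8 and 18.9 would set its severity to severe and its relationship to related.

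**The case against.** The strongest reply is that the documents agree with each other. The protocol defines a severity change as a new event and the SAP counts events so defined, so calling the total too high presupposes a definition by episode. No safety hypothesis is tested. Subject incidence, the usual basis for comparing arms, is already protected. Protocol 8.1.4 keeps ordinary fluctuation of disease symptoms out of the AE data, which removes one likely source of changing ocular records. The table specifications (SAP 1) and the CRF Completion Guidelines (Protocol 9.2) are separate documents and may contain a linking rule.

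Most of this stands, and it limits the point to descriptive event totals. It does not remove it: nothing in either document tells the programmer or the reader that a count of TEAEs is a count of severity segments, or that some segments are improvements.

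Three stronger readings are tempting, and the documents do not support them:

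- **That benefits are tabulated as TEAEs.** They are not AEs by the protocol's own definition. What is missing is an explicit exclusion.
- **That subject incidence is generally inflated.** It is not for post-dose events. For pre-dose events the worsening-only sentence may already settle the matter. The window is also short: AE collection starts at consent, which is on Day -1 or Day 1, and the first dose is on Day 1 (Protocol Table 1). Clinically significant slit lamp abnormalities at screening go to medical history (Protocol 7.2.3.2).
- **That a particular arm, or a particular percentage, is affected.** No rates of severity change are given.

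**Conclusion.** The point holds for event totals. Followed as written, the plan counts one post-dose episode 1 + *k* times and counts improvements as new TEAEs. The totals affected are those in the SAP 11.1 overall summary and, if produced as Protocol 9.9 plans, the numbers of TEAEs by SOC and preferred term.

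The size is unknown. The range of 1.25 to 2 times the number of episodes rests entirely on an assumed mean of 0.25 to 1 severity changes per event. Subject percentages for events starting after dosing do not change, and neither do the primary and key secondary tests.

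Two smaller gaps go with it. The handling of a pre-dose AE that eases after dosing is unclear, which should matter rarely. Benefit records have no stated exclusion from the TEAE tables. Overall this is a minor but easily corrected weakness in the descriptive safety reporting.

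**What to change.** In SAP 11.1:

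1. Define a TEAE as an AE that starts, or worsens in severity, after the first dose.
2. For event totals, link contiguous records of the same subject, preferred term and eye into one event, counted once at maximum severity. Say what contiguous means in dates. Say also how a record with an incomplete stop date is linked, because SAP 18.7 does not impute AE stop dates.
3. State that a record which only lowers the severity of a pre-dose event, and any record of an unexpected benefit, is listed but not tabulated.

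The timing-only definition also stands in Protocol 7.2.3.4 and the synopsis. Either align those, or declare the change in SAP Section 17, which at present lists only the added BCVA change from baseline.

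The cost is one SAP paragraph and a small programming step. Neither document describes a flag for benefit records, so finding them may need a manual review before database lock. No visit, assessment or AE recording rule changes, and the listings keep every record.

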8.1.2 Relationship Categorization

A physician/investigator must make the assessment of relationship to investigational product for each AE. The investigator should decide whether, in his or her medical judgment, there is a reasonable possibility that the event may have been caused by the investigational product. If there is no valid reason for suggesting a relationship, then the AE should be classified as “not related.” Otherwise, if there is any valid reason, even if undetermined or untested, for suspecting a possible cause-and-effect relationship between the investigational product and the occurrence of the AE, then the AE should be considered “related.” The causality assessment must be documented in the source document.

The following additional guidance may be helpful:

Term	Relationship Definition
Related	The temporal relationship between the event and the administration of the investigational product is compelling and/or follows a known or suspected response pattern to that product, and the event cannot be explained by the subject’s medical condition, other therapies, or accident.
Not Related	The event can be readily explained by other factors such as the subject’s underlying medical condition, concomitant therapy, or accident and no plausible temporal or biologic relationship exists between the investigational product and the event.

8.1.3 Outcome Categorization

The outcome of AEs must be recorded during the course of the study on the CRF. Outcomes are as follows:

- Fatal
- Not recovered/Not Resolved
- Recovered/Resolved
- Recovered/Resolved With Sequelae
- Recovering/Resolving
- Unknown

8.1.4 Symptoms of the Disease Under Study

Symptoms of the disease under study should not be classed as AEs as long as they are within the normal day-to-day fluctuation or expected progression of the disease and are part of the efficacy data to be collected in the study; however, significant worsening of the symptoms should be recorded as an AE.

8.1.5 Pregnancy

All pregnancies are to be reported from the time informed consent is signed until the defined follow-up period stated in Section 7.1.3.

Any report of pregnancy for any female study participant must be reported within 24 hours to the Shire Global Pharmacovigilance and Risk Management Department using the Shire Investigational and Marketed Products Pregnancy Report Form. A copy of the Shire Investigational and Marketed Products Pregnancy Report Form (and any applicable follow-up reports) must also be sent to the CRO/Shire medical monitor using the details specified in the emergency contact information section of the protocol. The pregnant female study participant must be withdrawn from the study.

Every effort should be made to gather information regarding the pregnancy outcome and condition of the infant. It is the responsibility of the investigator to obtain this information within 30 calendar days after the initial notification and approximately 30 calendar days postpartum.

Pregnancy complications such as spontaneous abortion/miscarriage or congenital abnormality are considered SAEs and must be reported using the Shire Clinical Study Serious Adverse Event and Non-serious AEs Required by the Protocol Form. Note: An elective abortion is not considered an SAE.

In addition to the above, if the investigator determines that the pregnancy meets serious criteria, it must be reported as an SAE using the Shire Clinical Study Serious Adverse Event and Non-serious AEs Required by the Protocol Form as well as the Shire Investigational and Marketed Products Pregnancy Report Form. The test date of the first positive serum/urine β -hCG test or ultrasound result will determine the pregnancy onset date.

8.1.6 Abuse, Misuse, Overdose, and Medication Error

Abuse, misuse, overdose, or medication error (as defined below) must be reported to the sponsor according to the SAE reporting procedure whether or not they result in an AE/SAE as described in Section 8.2. Note: The 24-hour reporting requirement for SAEs does not apply to reports of abuse, misuse, overdose, or medication errors unless these result in an SAE.

The categories below are not mutually exclusive; the event can meet more than 1 category:

- **Abuse** – Persistent or sporadic intentional intake of investigational product when used for a non-medical purpose (eg, to alter one's state of consciousness or get high) in a manner that may be detrimental to the individual and/or society
- **Misuse** – Intentional use of investigational product other than as directed or indicated at any dose (Note: This includes a situation where the investigational product is not used as directed at the dose prescribed by the protocol.)
- **Overdose** – Intentional or unintentional intake of a dose of an investigational product exceeding a pre-specified total daily dose of 4 drops per eye of the product.
- **Medication Error** – An error made in prescribing, dispensing, administration, and/or use of an investigational product. For studies, medication errors are reportable to the sponsor only as defined below.

Cases of subjects missing doses of the investigational product are not considered reportable as medication errors.

Medication errors should be collected/reported for all products under investigation.

The administration and/or use of the unassigned treatment is/are always reported as a medication error.

The administration and/or use of an expired investigational product should be reported as a medication error.

In cases of overdose, the investigator should determine if the medical monitor must be contacted for consultation.

Please refer to the Study Operations Manual for further details on reporting overdose and medication errors. An AE should only be reported if any of these events meets the definition of an AE as outlined in Section 8.1.

All investigational product provided to pediatric subjects should be administered or supervised by the parent(s)/guardian/legally authorized representative/caregiver.

8.2 Serious Adverse Event Procedures

8.2.1 Reference Safety Information

The reference for safety information for this study is the investigator's brochure, which the sponsor has provided under separate cover to all investigators.

